Title: Role of Platelet Rich Plasma in supporting the recovery of post-partum Levator Ani Muscle trauma

Running title: Platelet rich plasma in levator ani muscle trauma

NCT number: **NCT03021954**

Document date: January 15th, 2018

Financial dislaimer: None

STUDY PROTOCOL

Participant Flow

We obtained 245 primigravid women. As many as 85 subjects underwent caesarean section because of clinical indications, 39 subjects were failed to follow the study until the end and 5 subjects were found to have avulsion after 40 days post-partum. Overall, there were 58 subjects who successfully followed the examination until the end of the study.

Study Procedure

- a. All patients who come to Polyclinic in Public Health Center (Puskesmas) will be taken a history and physical examination to determine whether the patient meets the criteria or not,
- b. Patients who met the criteria were provided with information about this study. Patients who are willing will be asked to fill out an informed consent. If the patient refuses to participate in this study, the reasons for refusal must be written,
- c. Randomization was performed and participant were divided into 2 groups (intervention group and control group). Participant will not know the results of randomization. Participant may know the results of randomization at the end of the study,
- d. Initial data collection on study form and approval to participate will be taken. Participants are required to write down their full name, complete address, phone number, and family phone number. This is an attempt to increase the participation rate.
- e. Participant will be examined by ultrasound to assess pelvic floor biometry, perineometry to assess pelvic floor muscle strength,
- f. At delivery day, the participant in intervention group will be taken whole blood for preparation of 32 mL of PRP. After the PRP is ready, it will be injected directly into the levator ani muscle during post-partum perineorrhaphy,
- g. Participant in control group will still have whole blood taken for examination (complete blood count) but no PRP preparation will be carried out. During perrineorrharphy will be injected lidocaine 1%. In this way, it is hoped that the participant will now know that she is in the intervention or control group,

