Title: Role of Platelet Rich Plasma in supporting the recovery of post-partum Levator Ani Muscle trauma

Running title: Platelet rich plasma in levator ani muscle trauma

NCT number: NCT03021954

Document date: January 15th, 2018

Financial dislaimer: None

Study Analysis Plan (SAP)

• Estimated Sample Size

$$n1 = n2 = 2\left(\frac{(Z\alpha + Z\beta)S}{X1 - X2}\right)^2$$

Information:

n = Number of samples

 α = type I error is set at 5 %, the hypothesis is in the direction of $Z\alpha$ = 1.64

 β = type II error is set at 10 %, the hypothesis is in the direction of Z β = 1,28

X1 - X2 = the minimum difference that is considered significant

- Measurement of the levator hiatal area during valsalva, the researchers set a value of X1-X2 = 5. From the journal about the levator ani hiatus area during Valsalva, it was obtained SD = 6.09. The sample size for each group was 23 subjects.
- Measurement of the strength of the levator ani muscle contraction, the researchers set a value of X1-X2 = 9. From the journal on the strength of the levator ani muscle contraction, it was obtained that SD = 11.63. The sample size for each group was 27 subjects.
- The drop out number of samples is added by 20%. Thus, the total sample is 65 people.

Sampling Method

The sample was taken consecutively. The researcher took subjects who met the inclusion criteria and passed the exclusion criteria until the target number of subjects was met. Randomization using online randomizer. Subjects were divided into two groups, namely the intervention group with PRP injection and the control group.

Daya Analysis

Data were analyzed using Statistical Product and Service Solutions version 20 (SPSS version 20). Univariate analysis was performed for each variable and then presented in terms of frequency and percentage. For the bivariate analysis of the intervention and control groups with certain independent variables used unpaired categorical comparative

analysis of 2 groups using the Mann-Whitney test, paired comparative analysis of 2 groups using the Willcoxon test. If p < 0.25, then multivariate analysis was performed.

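### The arm is drawn before the step d approval, initial data and baseline measurements, and no concealment from the recruiter or perineometry operator is described

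*SAP*

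**What the plan says.** The SAP, under Sampling Method, describes consecutive recruitment: "The researcher took subjects who met the inclusion criteria and passed the exclusion criteria until the target number of subjects was met". On how arms are assigned it says only "Randomization using online randomizer". It does not say who operates the randomizer, whether the sequence is fixed beforehand, or how an assignment is released.

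The Protocol's Study Procedure gives a lettered order:

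- Step b: "Patients who are willing will be asked to fill out an informed consent". Reasons for refusal are recorded here.
- Step c: "Randomization was performed and participant were divided into 2 groups (intervention group and control group", followed by "Participant will not know the results of randomization".
- Step d: "Initial data collection on study form and approval to participate will be taken". Contact details are also taken.
- Step e: "Participant will be examined by ultrasound to assess pelvic floor biometry, perineometry to assess pelvic floor muscle strength".
- Step f: "At delivery day, the participant in intervention group will be taken whole blood for preparation of 32 mL of PRP". Step g gives the control procedure, also tied to the perineal repair.
- Step h: ultrasound and perineometry at 40 days and 3 months, with the ultrasound operator unaware of the group.

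**The concern.** Randomisation protects the comparison only if nobody who influences entry or measures baseline can act on the assignment. Here the assignment exists while two such activities are still to come.

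- **Entry.** Approval is recorded at step d, after the draw. If the person taking it knows the arm, whether a woman continues can depend on that arm.
- **Baseline strength.** Perineometry depends on effort: the operator asks the woman to squeeze as hard and as long as she can (Standard Operational Procedure 1, item 11). An operator who knows the arm can, without intending to, coach differently. A lower baseline in one arm would make its later recovery look larger.

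Neither problem can be repaired at analysis. A Mann-Whitney test takes the groups as given, and adjustment for a baseline measured after an unconcealed draw adjusts for a value that may itself carry the bias.

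**Working it through.** The point concerns the order of steps and who is masked, so the main check is a reading of the two documents side by side. The plan gives no figure to reproduce.

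**Order.** Consent form (b), draw (c), approval and initial data (d), baseline measurements (e), first use of the arm on delivery day (f, g). Nothing in d or e needs the arm. The draw could follow e without changing any other step.

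**Who is kept from knowing the arm.**

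- Participant: yes (step c, supported by the blood draw and lidocaine injection for controls in step g).
- Ultrasound operator: yes, stated in step h with the 40-day and 3-month visits. Step e is silent.
- Perineometry operator: not stated at any visit.
- Person taking step d approval and initial data: not stated.
- Person running the randomizer: not identified.

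**Consent.** Steps b and d place agreement on both sides of the draw. If b settles participation, the approval in d needs another meaning. If d settles it, the draw comes too early. The text does not decide between them.

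**Illustration of what is at stake.** Assume that dependence of entry on the arm leaves a prognosis gap of δ standard deviations favouring PRP, with no true effect, equal SDs and a normal approximation. With n per arm, the one-sided 5% false-positive rate is

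1 − Φ(1.645 − δ√(n/2)).

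For n = 29, √(29/2) = 3.808:

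- δ = 0.1: 1 − Φ(1.645 − 0.381) = 0.103
- δ = 0.2: 1 − Φ(1.645 − 0.762) = 0.189
- δ = 0.3: 1 − Φ(1.645 − 1.142) = 0.308

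On the SAP's strength SD of 11.63 these gaps are 1.2, 2.3 and 3.5 units, against the SAP's target difference of 9.

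The choice of 29 is half of the 58 finishers in the Protocol's Participant Flow. That section does not add up to 58: 245 − 85 − 39 − 5 = 116. With 58 per arm instead, the same formula gives 13%, 29% and 49%. However, 29 is also what the SAP's own formula yields for strength: 2 × ((1.64 + 1.28) × 11.63 / 9)² = 28.5, rounded up, where the SAP states 27.

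**The case against.** The best defence has four parts.

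1. **Consent comes first.** Step b takes informed consent and records refusals before the draw, and step d reads partly as enrolment paperwork. This stands. A reader might infer from step d that women are randomised before any consent; the documents do not support that. What remains is an unexplained second approval after the draw.

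2. **The ultrasound operator is masked, and ultrasound results are validated by a different expert.** This largely stands for ultrasound, although the masking is stated only with the follow-up visits. It does not reach perineometry, so the exposure of baseline values is clearest for strength.

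3. **Misuse of the randomizer is conjecture.** A reader might infer that the recruiter ran it and could repeat or look up a draw. The SAP says neither that nor the opposite. A list fixed in advance and properly held would also fit its sentence. The gap is that no safeguard is stated. Consecutive recruitment does not fill it, because it governs who is approached and not which arm a woman receives.

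4. **The steering figures restate an assumption.** This stands. No passage supports a gap of 0.1 to 0.3 SD, and a gap in the other direction would lower the rates to 2.1%, 0.8% and 0.3%. The draw also precedes delivery, when mode of birth and muscle trauma are unknown, which limits what a recruiter could foresee.

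A reader might also infer that a plain randomizer would leave the arms seriously unequal. The SAP does not say whether assignment was blocked, the count of finishers does not reconcile, and balance at enrolment would not secure balance among finishers after so many exclusions. That argument is not relied on here.

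**Conclusion.** The concern holds as a defect in a stated order, together with missing safeguards. The Protocol places the draw before approval, initial data and all baseline measurements without needing the arm until delivery, and the two documents describe no concealment from the staff who carry out step d or run perineometry. Late entry decisions and baseline strength can therefore depend on the arm.

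The documents do not show that staff knew the arm, that anyone was steered, or that a draw was repeated. The size of any bias is unknown. The rates of about 10%, 19% and 31% show only how sensitive a trial of this size is, under an assumed gap of 0.1 to 0.3 SD favouring PRP with 29 per arm. The conclusion rests on the lettered order being the order in which the steps are carried out.

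**What to change.** - Reorder the Study Procedure so that approval, initial data, and baseline ultrasound and perineometry are complete before the arm is drawn.
- Reconcile steps b and d, stating at which one participation is settled.
- Replace the SAP's single sentence with the mechanism: one sequence generated in advance, who generates and holds it, one assignment released per enrolled woman, and no redraw.
- State that the sequence and each assignment are concealed from the recruiter and from the ultrasound and perineometry operators, at baseline as well as at follow-up. Whoever must know the arm to prepare PRP can release it; the documents do not say who that is, so the role has to be named.

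The cost is protocol wording, one pre-generated list and minor logistics at release. The Protocol already reports participant flow to the end of the study, so the new order cannot help women already allocated. For them, the sponsor should state who ran the randomizer, whether the sequence was fixed beforehand, and who knew the arm at steps d and e. If concealment was in fact practised, a sentence or two would document it.

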- h. At 40 days and 3 months post- partum, the levator hiatal area was assessed using ultrasound examination and levator ani muscle strength was assessed by perineometry. The ultrasound operator does not know the patient group.

Standard Operational Procedure 1 - Perineometry Examination

- 1. Patient was asked to take off her pant and underwear, then wear what has been provided,
- 2. The perineometer tool used is Peritron TM, this tool has a vaginal sensor with T valve inflation, connecting tube, collar, and display unit,
- 3. Plug in the connecting tube to the display unit,
- 4. Activate Peritron TM by pressing the power button. The screen should shows at zero,
- 5. Select the appropriate mode using 3 WTS (3 way toggle switch). In DISPLAY mode, select NO to select numeric mode. Next in DEVICE mode, select PERI for measurement of pelvic floor muscle strength,
- 6. When using the vaginal sensor, grab the sensor at the tail of the connector on the connecting tube,

- 7. Sensor insertion was performed with the subject in the supine position and place pillow (1-2 pieces) on patient's head, knees formed 90 degrees, 45 degrees between the thighs and the examination bed, knees and feet separated by 30 cm,
- 8. The operator wears gloves. Insert the sensor (wrapped with a condom) until it leaves 1 cm in front of the vagina,
- 9. Then do inflation using a syringe on the T valve, inject air up to 100 cm. Pull back the plunger, turn the valve to position T and release the syringe,
- 10. Press and release the button on the display unit until it shows a zero,
- 11. Ask the subject to 'pinch' the sensor as hard and as long as possible,
- 12. Data will be stored in PEAK, AVERAGE, DURATION, GRADIENT, and AREA UNDER CURVE modes,
- 13. DURATION will be read in seconds, starting from pressure above 5 cmH₂O to below 5 cmH₂O,
- 14. AVERAGE is AREA UNDER CURVE/DURATION.
- 15. PEAK is the maximum value in cmH₂O unit,
- 16. GRADIENT is in cmH₂O. GRADIENT is the maximum value divided by the time it takes to reach the maximum value (to measure onset),
- 17. AREA UNDER CURVE is the length of contraction multiplied by the average value of muscle strength (AVERAGE),
- 18. Remove the sensor,
- 19. Wiping the subject's genital area and allowing the subject to change clothes.

Standard Operational Procedure 2 – Pelvic Floor Ultrasonography Examination

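### The SAP specifies no between-arm difference or confidence interval for hiatal area or contraction strength, and its frequency-and-percentage rule does not suit these numeric outcomes

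*SAP*

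**What the plan says.** The SAP's sample size section uses the formula for comparing two means. For the first outcome it says "Measurement of the levator hiatal area during valsalva, the researchers set a value of X1-X2 = 5", with an SD of 6.09. For contraction strength it uses a difference of 9 and an SD of 11.63. It defines these differences as the smallest that would count as important.

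The data analysis section then says "Univariate analysis was performed for each variable and then presented in terms of frequency and percentage", with no exception for numeric variables. For the comparison of the arms it "used unpaired categorical comparative" methods, continuing "analysis of 2 groups using the Mann-Whitney test, paired comparative analysis of 2 groups using the Willcoxon test". It ends: "If p < 0.25, then multivariate analysis was performed".

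The Protocol shows that both outcomes are measurements. Its study procedure reads "the levator hiatal area was assessed using ultrasound examination and levator ani muscle strength was assessed by perineometry", with the timing "At 40 days and 3 months post- partum". The perineometry procedure gives a physical scale, for example "PEAK is the maximum value in cmH₂O unit".

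**The concern.** The sizing and the analysis are on different scales. The sample size rests on a difference between means, and the SAP says how large that difference must be to matter. The analysis section asks for percentages and rank tests. A rank-test p-value says whether the arms differ, but not by how much. A table of percentages does not give a difference in area or pressure either.

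A sponsor that followed the SAP to the letter would therefore have no planned result to compare with 5 or 9. A small p-value could go with a difference well below those thresholds. A large one could go with an interval that still includes them. The reader could not tell which.

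**Working it through.** **1. What the documents provide for the two outcomes**

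| Element | Hiatal area | Contraction strength |
|---|---|---|
| Measured as | traced area on ultrasound (Protocol, SOP 2) | perineometer readings, e.g. PEAK in cmH₂O (Protocol, SOP 1) |
| Sized on (SAP) | mean difference 5, SD 6.09 | mean difference 9, SD 11.63 |
| Cut-points for categories | none | none |
| Summary planned (SAP) | frequency and percentage | frequency and percentage |
| Test planned (SAP) | Mann-Whitney, Wilcoxon | Mann-Whitney, Wilcoxon |
| Difference or confidence interval planned | none | none |

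The only cut-point in either document is the levator-urethral gap above 25 mm that defines avulsion. The SAP gives no units for 5 and 9, so the scale meant here is simply that of X1−X2.

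**2. The SAP's own sizing figures.** The formula is n = 2[(Zα + Zβ)S/(X1−X2)]², with Zα = 1.64 and Zβ = 1.28.

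- Area: 2 × (2.92 × 6.09/5)² = 25.3, so 26 per group; the SAP states 23.
- Strength: 2 × (2.92 × 11.63/9)² = 28.5, so 29 per group; the SAP states 27.
- Total: 2 × 27 × 1.2 = 64.8, which gives the stated 65.

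The shortfall per group is a separate matter. What counts here is that the formula is one for a difference in means.

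**3. What an interval would show.** The Protocol's participant flow reports 58 completers but not their arms; I assume 29 per arm. The standard error is S√(2/n).

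- Area: 6.09 × √(2/29) = 1.599. Half-width 1.96 × 1.599 = 3.13, or 3.20 with the t quantile on 56 degrees of freedom.
- Strength: 11.63 × √(2/29) = 3.054. Half-width 1.96 × 3.054 = 5.99, or 6.12 with t.
- At the planned 27 per group, the normal-quantile figures are 3.25 and 6.20.

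So an observed area difference of exactly 5 would come with an interval of about 1.8 to 8.2 (5 ± 3.20). An observed strength difference of exactly 9 would come with about 2.9 to 15.1 (9 ± 6.12). A significant test would thus leave open whether the threshold is met, and only the interval shows that. Adjustment for baseline would narrow these by √(1−r²), where r is the correlation between baseline and follow-up; the documents give no r.

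**4. What the named test costs in power.** Power is Φ(d√e/SE − z), where e is the efficiency relative to a comparison of means under normality: 1 for means, 3/π for Mann-Whitney, 2/π for a median split. Here d/SE is 5/1.599 = 3.126 for area and 9/3.054 = 2.947 for strength. The one-sided column matches the SAP's directional alpha (1.645; the SAP rounds it to 1.64). The two-sided column uses 1.96.

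| Analysis, 29 per arm | Two-sided: area / strength | One-sided: area / strength |
|---|---|---|
| Comparison of means | 87.8% / 83.8% | 93.1% / 90.4% |
| Mann-Whitney (named in the SAP) | 86.3% / 82.1% | 92.1% / 89.2% |
| Median split (hypothetical) | 70.3% / 65.2% | 80.2% / 76.0% |

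The named test costs under 2 percentage points. The last row describes a split that the documents do not plan.

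**The case against.** The strongest defence is that the wording is loose rather than wrong. Mann-Whitney and Wilcoxon rank ordinal or continuous values, no test of proportions is named, and no cut-points are given. The word categorical is therefore probably a slip, and the clause it sits in speaks of certain independent variables, so it may not concern the two outcomes at all. The measurements are recorded numerically, and nothing in the SAP forbids reporting means or a difference. The multivariate step might yield an estimate in the original units.

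Much of this stands. A reader might infer that area and strength will be dichotomised, with a heavy loss of power. The documents do not support that: they plan no split, and the tests they name work on uncategorised values. A reader might also infer that the trial is unable to produce an effect size. That goes too far as well, because the data will allow one; the SAP just does not specify it.

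The gap itself remains. If the clause is not about the outcomes, the SAP names no between-arm analysis of them at all, which is worse. The multivariate step is conditional on p < 0.25, and its model, outcome and covariates are unstated, so it cannot be relied on. That an estimate may be reported does not make it planned. An estimate chosen after the results are known leaves the visit, the measure and the method open to selection.

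**Conclusion.** The point holds as a mismatch between sizing and planned output. The SAP's summary rule does not suit its two numeric outcomes, and it specifies no between-arm difference or confidence interval to set against 5 and 9. The rank tests themselves are a valid choice, with a power cost of under 2 points under normality.

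The practical size is the information left out: intervals of roughly ±3.1 to 3.2 for area and ±6.0 to 6.1 for strength. These figures assume the SAP's SDs, 29 completers per arm and no baseline adjustment. The conclusion about the missing estimate rests on the text and does not depend on them.

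Median-split power losses should not be cited against this plan, except as a hypothetical. Even then, at the SAP's one-sided alpha, they would be about 93% to 80% for area and 90% to 76% for strength.

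**What to change.** - Restrict frequency and percentage to categorical variables such as avulsion, and remove the word categorical from the description of the outcome comparison.
- Summarise hiatal area and strength by arm and visit as mean (SD) and median (IQR), and analyse them uncategorised.
- For each outcome, report the baseline-adjusted mean difference (ANCOVA on the pre-delivery measurement) with a 95% confidence interval, and interpret it against 5 and 9. The mean difference is the natural choice because the sizing is in means. Mann-Whitney can stay as a supporting test.
- Name the visit (40 days or 3 months) and the perineometry measure that counts as strength. The Protocol stores five (peak, average, duration, gradient, area under the curve), and a difference can be compared with 9 only once one is chosen. State the units of 5 and 9.
- Confirm that the pre-delivery ultrasound and perineometry in the Protocol's study procedure record the same quantities as at follow-up, so that they can serve as covariates.

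This is a free improvement: it needs SAP wording and standard SPSS output, with no new visits or participants. The Protocol already reports the number of completers, so the outcome data may have been seen. If so, the change should be dated and identified as made after that point.

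### The SAP lists a within-woman Wilcoxon test beside the between-arm Mann-Whitney test and does not say which of them bears on a PRP effect

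*SAP*

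**What the plan says.** The SAP's data analysis section (printed there as Daya Analysis) covers the bivariate analysis in one sentence. It begins "For the bivariate analysis of the intervention and control groups with certain independent variables used unpaired categorical comparative", continues "analysis of 2 groups using the Mann-Whitney test", and then adds "paired comparative analysis of 2 groups using the Willcoxon test". A following sentence makes a multivariate analysis conditional on p < 0.25, without saying which test supplies that p-value or what the model contains.

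The Protocol's Study Procedure sets three measurement occasions:

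- **Step e**, listed before the delivery-day steps: "Participant will be examined by ultrasound to assess pelvic floor biometry, perineometry to assess pelvic floor muscle strength".
- **Step h**, two follow-up visits, with perineometry at the same times: "At 40 days and 3 months post- partum, the levator hiatal area was assessed using ultrasound examination".

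Step c randomises women to two groups. Steps f and g place the PRP or control injection at delivery, during the perineal repair.

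Neither document names a primary test, visit or analysis variable, or says which visits form the Wilcoxon pair.

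**The concern.** A paired test needs pairs. The two arms hold different women and no matching is described, so the only pairs available are two visits of the same woman. The Wilcoxon test therefore asks whether a measurement moved over time, in one arm or in all women together. That movement mixes any effect of PRP with the effects of birth, healing and time. The visits straddle delivery, and the study title presents PRP as an aid to recovery, so some shared change is a natural expectation.

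The SAP puts this test next to the one that does use the control arm and does not rank them. Two readings of the results would then be open and would mislead: that a significant change in the PRP arm shows PRP works, or that significance in the PRP arm but not in the control arm does. Neither compares the arms, and neither holds its error rate at 5% if there is any shared change.

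**Working it through.** **The plan's own figure.** There is none on this point. The documents give no size for change without treatment and no error rate for the paired test.

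**Inputs.**

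- Women per arm: 29. The Protocol's Participant Flow reports 58 women completing; an equal split, which is assumed, gives 58 / 2 = 29. The SAP's own 27 per group for strength gives nearly the same results (below).
- Level: two-sided 5%. The SAP's sample size section says "type I error is set at 5 %, the hypothesis is in the direction of" and uses 1.64, a one-sided value, but the analysis section does not state sidedness. A one-sided test in the direction of the shared change would raise the within-arm rates further.
- True PRP effect: none. Both arms have the same mean change.
- Shared change: 0.2, 0.36, 0.5 and 0.7 SD of the change score, with normal data. This is an assumption.

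**What these sizes mean in the SAP's units.** The SD of a change score is SD × √(2(1 − ρ)), where ρ is the within-woman correlation between visits. The documents do not give ρ. With ρ = 0.5 assumed, the factor is √1 = 1, so the change SD equals the SAP's SD:

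- Hiatal area: 0.2 × 6.09 = 1.2, up to 0.7 × 6.09 = 4.3, against a planned difference of 5.
- Strength: 0.2 × 11.63 = 2.3, up to 0.7 × 11.63 = 8.1, against a planned difference of 9.

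All settings are thus smaller than the difference the SAP treats as important.

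**Results with no PRP effect.** Simulated change scores were tested by Wilcoxon signed-rank in each arm and by Mann-Whitney between arms. Ranges show variation between runs.

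| Shared change (SD of change) | PRP arm significant | PRP significant, control not | Mann-Whitney on change |
|---|---|---|---|
| 0 | about 5% | about 5% | about 5% |
| 0.2 | 16–17% | about 14% | about 5% |
| 0.36 | about 44% | 24–25% | about 5% |
| 0.5 | 72–73% | 20–21% | about 5% |
| 0.7 | about 94% | 5–6% | about 5% |

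**Check on the third column.** If each independent arm is significant with probability p, the chance that PRP is significant and control is not is p(1 − p). For 0.36 SD this is 0.44 × 0.56 = 0.246; for 0.7 SD it is 0.94 × 0.06 = 0.056. The maximum is 0.5 × 0.5 = 25%. This error therefore rises and then falls as shared change grows, while the error in the second column only rises.

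**Check with 27 per arm.** Here the shared change was set as a fraction of the SAP's planned difference, with ρ from 0.3 to 0.7 and both outcomes. The PRP arm was significant in about 12–24% of trials at 25% of the difference, 36–73% at 50%, and 91–100% at 100%. Mann-Whitney on change stayed between 3.6% and 5.7%.

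**Which between-arm contrast.** The injection is given at delivery, so the 40-day value is already post-treatment. Suppose PRP shifts hiatal area by 5 by day 40 and the shift persists at 3 months. The expected arm difference in the 40-day to 3-month change is 5 − 5 = 0, so that contrast rejects in about 5% of trials. With 29 per arm, SD 6.09 and ρ = 0.5 assumed, Mann-Whitney on change from the pre-delivery value has about 83–84% power. Follow-up adjusted for that value has about 94%.

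**The case against.** The strongest reply is that the plan already contains a valid test. The sentence opens with the intervention and control groups and names Mann-Whitney first. The sample size formula is for two independent groups, and the trial is randomised with an injected control. Comparing follow-up values between randomised arms removes shared change in expectation, so a change score is not needed for validity. All of this stands.

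A reader might infer that the trial's efficacy claim rests on the Wilcoxon test, that natural recovery will be credited to PRP, or that no between-arm comparison of change is planned. The documents do not support any of these. The SAP never says what the Wilcoxon result will be used for, and it leaves open whether Mann-Whitney is applied to change or to visit values. That is unspecified, not absent.

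It is also fair to say that change without treatment is only implied, by the title and by the timing of the visits. Its size cannot be taken from the documents. The logic does not depend on the size: a within-arm test has no control for shared change, whatever its amount.

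The conditional multivariate analysis does not settle the matter, because neither its trigger nor its model is defined.

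**Conclusion.** The point holds as a gap in specification with a real consequence. The SAP sets a test that cannot isolate PRP beside one that can, and nothing says that only the second counts. How far a within-arm result would mislead depends on the assumed shared change, normal data, 29 per arm and a two-sided 5% level. Over 0.2 to 0.7 SD, false significance in the PRP arm runs from about 16% to 94%. The pattern of PRP significant and control not runs from about 5% to 25%. With no shared change, the within-arm rate is the nominal 5%. The between-arm comparison of change stays near 5% throughout.

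This is worth correcting before analysis. It does not show that the trial's conclusion would be wrong.

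**What to change.** Amend the SAP's data analysis section as follows:

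1. Name the between-arm comparison as the only test of a PRP effect, for each outcome, at one stated follow-up visit (for example 3 months).
2. Use the step e measurement as baseline, either by adjusting the follow-up value for it or by applying Mann-Whitney to the change from it. Adjustment is the safer choice. Relative to the variance of the follow-up value alone, a change score has variance 2(1 − ρ), which exceeds 1 when ρ is below 0.5, whereas the adjusted value has about 1 − ρ².
3. Report the estimated difference with its 95% CI, and state whether the test is one-sided or two-sided.
4. Do not use the 40-day to 3-month change as the main contrast, for the reason shown above.
5. Define the Wilcoxon pairs, report those results as a description of the course within each arm, and state that a difference between the two arms' within-arm p-values is not evidence of a PRP effect.

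The cost is a few sentences and one computed variable or model. No new data are needed, provided step e recorded hiatal area and strength in the same way as the follow-up visits. Step e refers to pelvic floor biometry in general terms, so the SAP should confirm this.
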